**Cycle 1-2**

	≥ 1	2000 mg/m  /dose once daily	Use eye drops as described in Section 5.2
--	-----	---	---

**NOTE;**The choice of intrathecal therapy, between cytarabine or cytarabine/methotrexate/hydrocortisone on Day 0 and on subsequent days for patients with CNS2 and CNS3 is at the discretion of the treating physician. CNS2 and CNS3 patients will receive additional IT cytarabine OR IT triples once weekly until the CNS is clear of blasts on 2 consecutive LPs, with a minimum of 4 IT cytarabine OR IT Triples doses administered (maximum of 6 intrathecal treatments).

Assigned Dose Level \_\_\_\_\_ Ht \_\_\_\_\_ cm Wt \_\_\_\_\_ kg BSA \_\_\_\_\_ m^2

Date Due	Date Given	Day	IT ARAC _____mg	IT Triples ARAC____mg MTX____mg HC____mg	LCV PO/IV _____mg	GMI-1271 IV _____mg	FLU IV _____mg	HD ARAC IV _____mg	Studies
Enter calculated dose above and actual dose administered below									
		PRE	_____mg^	_____mg^ _____mg^ _____mg^					a-k, m
		1			_____mg% _____mg%	_____mg			n
		2				_____mg _____mg	_____mg	_____mg	
		3				_____mg _____mg	_____mg	_____mg	
		4				_____mg _____mg	_____mg	_____mg	d
		5				_____mg _____mg	_____mg	_____mg	
		6				_____mg _____mg	_____mg	_____mg	n
		7	_____mg*	_____mg* _____mg* _____mg*		_____mg _____mg			a, d-g, m
		8			_____mg% _____mg%	_____mg _____mg			
		9							
		10							
		11							d
		12							
		13							
		14	_____mg*	_____mg* _____mg* _____mg*					a, d-g, m
		15			_____mg% _____mg%				
		16							
		17							d
		18							
		19							
		20							
		21	_____mg*	_____mg* _____mg* _____mg*					a, d-g, m
		22			_____mg% _____mg%				
		23							
		24							d
		25							
		26							
		27							
		28	_____mg^	_____mg^ _____mg^ _____mg^					a, b, d- h, l-m, o
		29			_____mg% _____mg%				

Please refer to [Section 8.1](#) for the specific timing of these observations.

**Cycle 1-2**

## Required Observations

- a. History, Physical exam (including VS). Prior to Cycle 1 and every week during Cycle 1. Prior to Cycle 2 and as clinically indicated during Cycle 2.
- b. Wt /Ht/BSA. Prior to Cycle 1 and prior to Cycle 2.
- c. Performance Status. Prior to Cycle 1 and prior to Cycle 2.
- d. CBC/diff/platelets. Prior to Cycle 1 and twice weekly during Cycle 1. Prior to Cycle 2 and as clinically indicated during Cycle 2.
- e. Electrolytes including Ca++, Mg++, PO4. Prior to Cycle 1 and weekly during Cycle 1. Prior to Cycle 2 and as clinically indicated during Cycle 2.
- f. Creatinine. Prior to Cycle 1 and weekly during Cycle 1. Prior to Cycle 2 and as clinically indicated during Cycle 2.
- g. ALT, AST, bilirubin. Prior to Cycle 1 and weekly during Cycle 1. Prior to Cycle 2 and as clinically indicated during Cycle 2.
- h. Albumin. Prior to Cycle 1 and prior to Cycle 2.
- i. Pregnancy test and Urinalysis. Prior to Cycle 1. As clinically indicated during Cycle 2.
- j. ECHO or gated radionuclide study. Prior to Cycle 1 and prior to Cycle 2 .
- k. EKG. Prior to Cycle 1 and prior to Cycle 2.
- l. Bone marrow aspirate. End of Cycles 1-2 may be performed between Days 28-35. See [Section 8.2](#) for details.
- m. CSF for cell count, cytospin. Prior to Cycle 1, with every LP, and end of Cycle 1-2.
- n. Pharmacokinetics. See [Section 8.3](#) for timing details
- o. Radiographic evaluation of extramedullary disease, if applicable. End of Cycles 1-2 may be performed between Days 28-35. See [Section 12.4](#) for details.

THIS PROTOCOL IS FOR RESEARCH PURPOSES ONLY, SEE PAGE 1 FOR USAGE POLICY

## 6.0 DOSE MODIFICATIONS FOR ADVERSE EVENTS

**The Study Chair must be notified of any dosage modification.**

In the event that one study drug is held or delayed for toxicity, all systemic chemotherapy should be held or delayed. For guidance on intrathecal therapy, see [Section 6.3.1.2](#).

### 6.1 Dose Modifications for Hematological Toxicity

6.1.1 Patients who experience a hematologic dose limiting toxicity defined as failure to recover a peripheral blood ANC > 200/ $\mu$ L and non-transfusion dependent platelet count > 20,000/ $\mu$ L by 43 days after the start of the cycle, not due to malignant infiltration or severe infection will be allowed to proceed to Cycle 2 at the next lower dose level at the discretion of the treating physician and study chair or vice-chair. If patient is starting at Dose Level -1, further de-escalation will not occur and the patient must be removed from protocol therapy.

### 6.2 Dose Modifications for Non-Hematological Toxicity

6.2.1 Patients who have any dose-limiting non-hematological toxicity (as defined in [Section 5.5.1](#)) may continue on protocol therapy upon meeting eligibility lab requirements (see [Section 4.0](#)) or Grade  $\leq 2$  but should receive subsequent doses at the next lower dose level. If patient is starting at Dose Level -1, further de-escalation will not occur and the patient must be removed from protocol therapy.

6.2.2 If a non-hematological dose-limiting toxicity recurs after one dose reduction, the patient must be removed from protocol therapy.

6.2.3 Patients who have a dose-limiting non-hematological toxicity that does not resolve to Grade  $\leq 2$  or eligibility within 43 days after the start of the cycle, must be removed from protocol therapy.

### 6.3 Modifications and supportive care recommendations for toxicity related to standard therapy

#### 6.3.1 Neurological Toxicity

##### 6.3.1.1 Cytarabine

The most common neurotoxicity related to fludarabine or cytarabine administration is an acute cerebellar syndrome that may manifest itself as ataxia, nystagmus, or dysarthria. However, seizures and encephalopathy have also occurred following therapy with high dose cytarabine. Patients experiencing Grade 3 or 4 CTCAE version 5.0 nervous system disorders should be removed from protocol therapy.

##### 6.3.1.2 Intrathecal Chemotherapy

This protocol will utilize intrathecal triples (ITT) including methotrexate, hydrocortisone and cytarabine. Experience with ITT in ALL therapy demonstrates that there is a risk for methotrexate induced leukoencephalopathy. The timing of this toxicity often occurs 1-2 weeks after intrathecal administration. This CNS toxicity may present with a wide range of symptoms and severity. Seizures or

THIS PROTOCOL IS FOR RESEARCH PURPOSES ONLY, SEE PAGE 1 FOR USAGE POLICY

transient stroke-like symptoms (weakness, hemiparalysis, aphasia) are most common but more severe encephalopathies are possible. There is no standard management approach and clinical judgment by the treating physician of each individual case is required for management. In general, evaluation of systemic disorders or infection (blood cultures, electrolytes, organ function and/or examination of the CSF) is important to exclude other contributing factors. Brain imaging is often helpful. Generally CT scans are normal. MRI abnormalities may be present (although sometimes these findings lag behind clinical manifestations) and may show findings consistent with posterior reversible encephalopathy or other white matter changes. The benefit of treatment with dextromethorphan remains unproven but may be used per the treating physician's discretion.

For patients who experience neurologic toxicity following intrathecal therapy, the treating physician has several options for future intrathecal treatments. In patients with ongoing neurologic symptoms, it is reasonable to hold or delay the subsequent intrathecal treatment(s) to allow recovery. In patients who have improvement of the CNS toxicity, the treating physician should consider the severity and duration of symptoms to decide whether to continue ITT as scheduled in protocol therapy or to replace the ITT with IT cytarabine.

In cases where the decision is to proceed with additional ITT, it is recommended to include leucovorin rescue with the subsequent intrathecal treatment at a dose of 5 mg/m^2 IV/PO x 2 doses at 24 and 30 hours after the LP.

In cases where the decision is made to replace with IT cytarabine, the following doses should be used (based on prior COG AML protocols including AAML1031): Intrathecal Cytarabine Age-based dosing:

**Table 6 – Intrathecal Cytarabine Age-based Dosing**

Age	Dose
< 1 year	20 mg
≥ 1 to < 2 years	30 mg
≥ 2 to < 3 years	50 mg
≥ 3 years	70 mg

If the event does not recur, resumption of ITT therapy should be considered for subsequent intrathecal therapy.

For patients who do not return to their pre-event baseline neurological status or for those with recurrent events, or evidence of progressive encephalopathy, additional evaluations may be warranted and the treating physician may consider a more prolonged or definitive change in therapy.

## 6.3.2 Renal Toxicity

### 6.3.2.1 Cytarabine

Patients with nephrotoxicity secondary to antibiotics, or antifungals, may have prolonged excretion of cytarabine leading to more severe marrow and extramedullary toxicity.

THIS PROTOCOL IS FOR RESEARCH PURPOSES ONLY, SEE PAGE 1 FOR USAGE POLICY

- Patients with a serum creatinine  $> 2$  mg/dL or  $> 2\times$  normal for age should be hydrated orally or intravenously. Following hydration, the patient must have a creatinine clearance  $\geq 60$  mL/min/1.73m^2 as measured preferably by a nuclear GFR scan, timed urine collection for creatinine clearance, or calculated by the Schwartz formula before proceeding with cytarabine therapy.
- If the creatinine clearance is abnormal ( $< 60$  mL/min/1.73m^2) then Cycle 2 high dose cytarabine should be reduced by 50% for each daily dose. With this approach, previous research has shown the prevention of subsequent neurotoxicity in recipients of high dose cytarabine in the face of renal insufficiency.

### 6.3.2.2 Fludarabine

Renal clearance accounts for about 40% of the total body clearance of fludarabine and clearance of the primary active metabolite is decreased in patients with renal impairment. Renal elimination appears to become more important at high dosages of the drug. The dose of fludarabine needs to be adjusted in patients with moderate renal impairment. The following are suggested guidelines for dose adjustment of fludarabine in renal impairment:

**Table 7 – Fludarabine Dosing Guidelines**

Creatinine Clearance mL/min/1.73m 	Daily Fludarabine Dose
$> 70$	No adjustment required
30-70	Administer 80% of calculated dose
$\leq 30$	Withhold Fludarabine
Hemodialysis	Administer 25% of calculated dose
Continuous ambulatory peritoneal dialysis (CAPD)	Not recommended
Continuous renal replacement therapy (CRRT)	Administer 80% of calculated dose 

## 6.3.3 Rash

### 6.3.3.1 Cytarabine

- **Hand-Foot Syndrome**

Hand-foot syndrome has been reported in patients treated with high-dose cytarabine. Patients who develop hand-foot syndrome may receive topical emollients (such as Aquaphor) as well as topical or systemic steroids or antihistamines if appropriate. Oral administration of vitamin B6 (pyridoxine) can also be used for these patients- BSA  $< 0.5$  m^2: 50 mg per day; BSA 0.5-1 m^2: 100 mg per day; BSA 1.1-1.5 m^2: 200 mg per day, and BSA  $> 1.5$  m^2: 300 mg per day.

- **Ara-C Syndrome including Fever, Rash, or Conjunctivitis**

Do not withhold cytarabine for fever if it is likely to have been caused by the cytarabine. However, blood cultures should be obtained even if fever is thought to be likely due to cytarabine. Institution of antibiotics for fever associated with cytarabine infusion is at the discretion of the treating physician (see fever management recommendations in the COG Supportive Care Guidelines). For rash or conjunctivitis, withhold cytarabine for Grade 3-4 toxicity until resolved to  $\leq$  Grade 1. Make up missed doses and consider concurrent treatment with hydrocortisone or

Page 35

THIS PROTOCOL IS FOR RESEARCH PURPOSES ONLY, SEE PAGE 1 FOR USAGE POLICY

dexamethasone, and/or with dexamethasone ophthalmic drops for conjunctivitis only.

## 7.0 SUPPORTIVE CARE AND OTHER CONCOMITANT THERAPY

### 7.1 Concurrent Anticancer Therapy

Concurrent cancer therapy other than protocol therapy, including chemotherapy, radiation therapy, immunotherapy, or biologic therapy may NOT be administered to patients receiving study drug. If these treatments are administered the patient will be removed from protocol therapy.

### 7.2 Investigational Agents

No other investigational agents may be given while the patient is on study.

### 7.3 Supportive Care

Appropriate antibiotics, blood products, antiemetics, fluids, electrolytes and general supportive care are to be used as necessary. Please see COG Supportive Care guidelines at <https://childrensoncologygroup.org/index.php/cog-supportive-care-guidelines>. See [Section 7.5](#), “Concomitant Medications” for drugs that should not be used concomitantly due to potential interactions with uproleselan (GMI-1271).

#### Hospitalization/Hospital Environment

Hospitalization following each course of chemotherapy is strongly recommended until the absolute phagocyte count (sum of the neutrophils, bands and monocytes) is rising for 2 successive days, and the patient is afebrile and clinically stable. An additional discharge criterion of an absolute neutrophil count (ANC) of at least 200/μL is also suggested.

It is recommended that patients should be assigned to rooms with special air filtration systems such as high efficiency particulate air filters (HEPA) or clean-air rooms with constant positive pressure airflow if at all possible.

#### Infectious Diseases Prophylaxis

In an effort to decrease the rates of infection, prophylactic antimicrobials and antifungals are strongly encouraged as outlined below. Signs and symptoms of infection (including fever) should prompt rapid switch from prophylactic treatment to empiric or directed therapy.

#### Antifungal Prophylaxis

The COG trial ACCL0933 compared prophylactic treatment with caspofungin versus fluconazole during chemotherapy treatment for AML in children and adolescents. The echinocandins, (eg., micafungin, caspofungin) have extensive safety and dosing studies in children, and they have both anti-yeast and anti-mold activity (covering both *Candida* and *Aspergillus* species which are the more common causes of fungal infection in children receiving AML therapy). ACCL0933 demonstrated that the five-month cumulative incidence of proven or probable invasive fungal disease was significantly lower in those treated with caspofungin compared to fluconazole (3.1% vs. 7.2%; p=0.03). A reduction in invasive *aspergillus* seemed to account for the majority of the difference in invasive fungal infection rates between the two groups.

THIS PROTOCOL IS FOR RESEARCH PURPOSES ONLY, SEE PAGE 1 FOR USAGE POLICY

**On the current protocol, it is strongly encouraged that patients receive antifungal prophylaxis.** Data from ACCL0933 supports prophylaxis with an echinocandin such as caspofungin or micafungin. Prophylaxis dosing is per institutional standard, but on ACCL0933 caspofungin was administered starting 1-3 days after completion of the systemic chemotherapy and continued until demonstration of ANC recovery ( $>100\text{-}500/\mu\text{L}$ ) after nadir. Intravenous dosing of caspofungin used on the trial was as follows:

Caspofungin IV  $70\text{ mg}/\text{m}^2/\text{day}$  on day 1 (max  $70\text{ mg}/\text{day}$ ) followed by  $50\text{ mg}/\text{m}^2/\text{day}$  (max dose  $50\text{ mg}/\text{day}$ ).

The use of azole antifungals is permitted per treating physician discretion.

#### Antibacterial Prophylaxis

Bacterial infections, including bacteremia, are common during AML therapy. The COG trial ACCL0934 randomly assigned participants to levofloxacin prophylaxis versus no antibiotic prophylaxis and compared the rates of infection in patients undergoing 2 courses of treatment for acute leukemia (AML and relapsed ALL) or those receiving a hematopoietic stem cell transplant (HSCT). The study was stopped early at an interim analysis due to the significantly decreased rate of bacteremia within the acute leukemia group for those who received levofloxacin versus those without prophylaxis (21.9% vs 43.4%; risk difference, 21.6%; 95%CI, 8.8%-34.4%,  $P = 0.001$ ). In secondary analysis, the trial also reported that patients in the levofloxacin prophylaxis group were less likely to have fever and neutropenia and less likely to test positive for *C. Difficile* (likely due to less need for broad spectrum antibiotics for empiric treatment). There were no significant differences in invasive fungal disease or musculoskeletal toxic effects at 2 months or 12 months. Importantly, among bacteremia isolates there was no evidence of increased antimicrobial resistance in the levofloxacin group other than resistance to levofloxacin/fluoroquinolones.

**Thus, on the current protocol, it is strongly encouraged that patients receive antibiotic prophylaxis and preferably with levofloxacin.**

On ACCL0934, levofloxacin was administered starting on day 1 of each chemotherapy treatment course and continued until evidence of count recovery ( $\text{ANC} > 200/\mu\text{L}$  after nadir). Levofloxacin can be dosed per institutional standards. ACCL0934 utilized the following levofloxacin dosing:

- Age 6 months to  $< 5$  years: Levofloxacin PO/IV  $10\text{ mg}/\text{kg}$  twice daily
- Age  $\geq 5$  years: Levofloxacin PO/IV  $10\text{ mg}/\text{kg}$  once daily with maximum dose of  $750\text{ mg}/\text{day}$

#### **7.4 Use of myeloid growth factor support**

The use of a myeloid growth factor (GCSF or GM-CSF) is not required and can be used at the discretion of the treating physician. The use of PEGfilgrastim is not permitted.

#### **7.5 Concomitant Medications**

To minimize the risk of neurotoxicity, it is recommended but not required that intrathecal therapy is administered at least 24 hours before or after systemic chemotherapy.

Because there is a potential for interaction of uproleselan (GMI-1271) with other concomitantly administered drugs, the case report form must capture the concurrent use of all other drugs, over-the-counter medications, or alternative therapies during Cycle 1. Uroleselan is a substrate for the efflux transporters P-gp and MRP2, may be a weak substrate for BCRP. Strong inhibitors of these efflux transporters (eg.,

THIS PROTOCOL IS FOR RESEARCH PURPOSES ONLY, SEE PAGE 1 FOR USAGE POLICY

amiodarone, azithromycin, carvedilol, clarithromycin, cyclosporine, delavirdine, dronedarone, efavirenz, eltrombopag, emtricitabine, itraconazole, ketoconazole, lapatinib, lopinavir and ritonavir, probenecid, propafenone, quinidine, ranolazine, ritonavir, saquinavir and ritonavir, telaprevir, tipranavir and ritonavir, verapamil) should be used with caution or avoided if reasonable alternatives exist. The study chair and/or vice chair should be alerted if the patient is taking any agent known to affect or with the potential for drug interactions. The study team should check a frequently updated medical reference for a list of drugs to avoid or minimize use of. [Appendix X](#) – Patient Drug Interactions Handout and Wallet Card should be provided to patients.

## 8.0 EVALUATIONS/MATERIAL AND DATA TO BE ACCESSIONED

Timing of protocol therapy administration, response assessment studies, and surgical interventions are based on schedules derived from the experimental design or on established standards of care. Minor unavoidable departures (up to 72 hours) from protocol directed therapy and/or disease evaluations (and up to 1 week for surgery) for valid clinical, patient and family logistical, or facility, procedure and/or anesthesia scheduling issues are acceptable (except where explicitly prohibited within the protocol)

### 8.1 Required Clinical, Laboratory and Disease Evaluation

All clinical and laboratory studies to determine eligibility must be performed within 7 days prior to enrollment unless otherwise indicated. Laboratory values used to assess eligibility (see [Section 4.0](#)) must be no older than seven (7) days at the start of therapy. Laboratory tests need not be repeated if therapy starts within seven (7) days of obtaining labs to assess eligibility. If a post-enrollment lab value is outside the limits of eligibility, or laboratory values are older than 7 days, then the following laboratory evaluations must be re-checked within 48 hours prior to initiating therapy: CBC with differential, bilirubin, ALT (SGPT), AST, and serum creatinine. If the recheck is outside the limits of eligibility, the patient may not receive protocol therapy and will be considered off protocol therapy. Imaging studies, bone marrow biopsy and/or aspirate, biopsy of extramedullary site (if the bone marrow is not involved by disease) and lumbar puncture must be obtained within 14 days prior to enrollment.

**Table 8 – Required Clinical, Laboratory and Disease Evaluation**

STUDIES TO BE OBTAINED (Phase 1 Cohort)	Pre- Study	During Cycle 1	Prior to Cycle 2	During Cycle 2
History	X	Weekly	X 	
Physical Exam with vital signs	X	Weekly	X 	X 
Height, weight, BSA	X		X 	
Performance Status	X			X 
CBC, differential, platelets 	X	Twice Weekly (every 3 to 4 days) 	X 	X 
Electrolytes including Ca ++ , PO 4 , Mg ++	X	Weekly	X 	X 
Creatinine, ALT, bilirubin	X	Weekly	X 	X 
Albumin	X		X 	
Pregnancy Test 	X			X 
Urinalysis	X			X 

THIS PROTOCOL IS FOR RESEARCH PURPOSES ONLY, SEE PAGE 1 FOR USAGE POLICY

ECHO or gated radionuclide study	X		X 	
EKG	X		X 	
Bone Marrow Aspirate for flow cytometry and MRD assessment. See Section 8.2	X	End of Cycle 1		End of cycle 2
Radiologic assessment of extramedullary disease, if applicable	X	End of Cycle 1		End of Cycle 2
CSF for cell count and cytospin	X	With every LP		End of cycle 2
Pharmacokinetics See Section 8.3 for timing		X		
 If patients develop Grade 4 neutropenia or thrombocytopenia, CBC/differential/platelets should be checked every 3 to 4 days until recovery to Grade ≤ 3.  Women of childbearing potential require a negative pregnancy test prior to starting treatment; See Section 4.2.2  Studies may be obtained within 72 hours prior to the start of the subsequent cycle.  As clinically indicated.				

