### 4.2.2 Pregnancy or Breast-Feeding

Pregnant or breast-feeding women will not be entered on this study due to risks of fetal and teratogenic adverse events as seen in animal/human studies, OR because there is yet no available

THIS PROTOCOL IS FOR RESEARCH PURPOSES ONLY, SEE PAGE 1 FOR USAGE POLICY

information regarding human fetal or teratogenic toxicities. Pregnancy tests must be obtained in girls who are post-menarchal. Males or females of reproductive potential may not participate unless they have agreed to use two effective methods of birth control, including a medically accepted barrier or contraceptive method (eg, male or female condom) for the duration of the study and for 3 months after the last dose of uproleselan (GMI-1271). Abstinence is an acceptable method of birth control.

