## 5.2 **Criteria for Starting Subsequent Cycles**

A cycle may be repeated every 28 days up to 2 total cycles if the patient; 1) has at least stable disease; and, 2) all pre-cycle studies required per [Section 8.1 are obtained](#) and eligibility criteria as defined in [Section 4.0 are met](#); and, 3) is otherwise eligible to continue agent administration per the requirements in [Section 6.0](#)

For patients in MRD negative remission, it is required that patients have an ANC >200/μL or a sustained platelet count >20,000/μL before proceeding with cycle 2.

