### 5.5.2.2 **Note:** Grade 3 or 4 febrile neutropenia will not be considered a dose-limiting toxicity.

## 5.6: THERAPY DELIVERY MAPS (TDMS) FOR CYCLE 1-2

**Therapy Delivery Map – Cycle 1-2** A cycle of therapy is considered to be 28 days. A cycle may be repeated for a total of 2 cycles, up to a total duration of therapy of approximately 2 months. Refer to [section 4.1](#) for eligibility criteria to start cycle 1. For patients in MRD negative remission, it is required that patients have an ANC >200/ $\mu$ L or a sustained platelet count >20,000/ $\mu$ L before proceeding with cycle 2.

This form is to be completed and uploaded into RAVE at the end of every cycle.

Accession #

Patient COG ID number

Institution

Extensive details are in [Section 5.1](#) (treatment overview). This TDM extends to three pages.

DRUG	ROUTE	DOSAGE	DAYS	IMPORTANT NOTES																				
IT Cytarabine (AraC)	Intrathecal (IT)	Age-based dosing: 

Age	Dose	

< 1 year	20 mg	

≥ 1 to < 2 years	30 mg	

≥ 2 to < 3 years	50 mg	

≥ 3 years	70 mg	

	Age	Dose	< 1 year	20 mg	≥ 1 to < 2 years	30 mg	≥ 2 to < 3 years	50 mg	≥ 3 years	70 mg	Days 0 ^ , 7*, 14*, 21*, 28 ^	
^All patients. First time point given at the time of diagnostic lumbar puncture OR Day 0 for all patients. Note that Day 28 LP with IT chemotherapy of Cycle 1 counts as Day 0 LP with IT of Cycle 2. If the patient received IT cytarabine or triple IT therapy during their diagnostic workup within 14 days of starting protocol therapy, then they do not need additional Day 0 IT therapy.
 
*CNS 2/3 patients ONLY.
 
A minimum of 4 and a maximum of 6 weekly (count includes day 0 IT) intrathecal treatments may be given. The choice between IT Cytarabine OR IT Triples is up to the treating physician's discretion. See Section 5.1 for administration guidelines.
										
Age	Dose																							
< 1 year	20 mg																							
≥ 1 to < 2 years	30 mg																							
≥ 2 to < 3 years	50 mg																							
≥ 3 years	70 mg																							

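### No pregnancy test is clearly required before Cycle 2, although pregnancy bars uproleselan and requires removal from therapy

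*Combined protocol and SAP*

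**What the plan says.** **Rules on pregnancy.** Section 4.2.2 excludes pregnant patients at entry and adds: "Pregnancy tests must be obtained in girls who are post-menarchal". Section 9.1.8 forbids giving uproleselan to pregnant or lactating women. Section 10.1(i) lists pregnancy as a criterion for removal from protocol therapy.

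**Rules on starting Cycle 2.** Section 5.2 states: "A cycle may be repeated every 28 days up to 2 total cycles". Among its conditions are that the Section 8.1 pre-cycle studies are done and that the "eligibility criteria as defined in" Section 4.0 are met. The text under Table 1 is narrower and asks only that the organ function criteria be met.

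**The schedule.** In Table 8 the pregnancy test is marked Pre-Study, is blank under During Cycle 1 and Prior to Cycle 2, and is marked as clinically indicated under During Cycle 2. Footnote 2 reads: "Women of childbearing potential require a negative pregnancy test prior to starting treatment". Footnote 3, which governs the items that are repeated before Cycle 2, reads: "Studies may be obtained within 72 hours prior to the start of the subsequent cycle".

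**The Therapy Delivery Map (Section 5.6).** Item i reads: "Pregnancy test and Urinalysis. Prior to Cycle 1. As clinically indicated during Cycle 2". The grid, which serves both cycles, lists items a–k and m in its PRE row and so nominally includes item i. The grid sends the reader to Section 8.1 "for the specific timing of these observations". The TDM is not optional: "This form is to be completed and uploaded into RAVE at the end of every cycle".

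**The concern.** The protocol has a standing prohibition on dosing in pregnancy, but its schedule contains no required step that would detect a pregnancy arising during Cycle 1. Removal under 10.1(i) works only once a pregnancy is known. A site that followed Table 8 and TDM item i to the letter would start a second course of three drugs on the pre-Cycle 1 result.

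The protocol itself states what is at stake. Table 10 notes fetal harm and teratogenicity in humans with cytarabine. Table 13 reports embryo death and malformation in rats and rabbits with fludarabine. Section 2.2.4 says that reproductive and developmental toxicity studies of uproleselan have not been done. This is a patient-safety gap in the schedule. It does not touch sample size or the dose-finding rules.

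**Working it through.** The plan gives no figure of its own here, so the check is a comparison of sections plus the age of the last required test.

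**1. Is the test an isolated omission?** Table 8 marks 15 items Pre-Study.
- Nine are repeated under Prior to Cycle 2: history; physical examination; height, weight and BSA; CBC; electrolytes; creatinine, ALT and bilirubin; albumin; ECHO; EKG.
- Three are covered during or at the end of Cycle 1: marrow, imaging and CSF.
- That leaves 15 − 9 − 3 = 3: performance status, urinalysis and the pregnancy test.

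Urinalysis is not a Section 4.0 criterion. Performance status is one, but TDM item c requires it before Cycle 2. The pregnancy test is the only Section 4.0 item required before Cycle 2 by neither Table 8 nor the TDM item text.

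**2. How old is the last required test at Cycle 2 Day 1?** The inputs are a 28-day cycle (Section 5.1), eligibility laboratory values no more than 7 days old at the start of therapy (Section 4.0), eligibility studies within 7 days before enrollment (Section 8.1), and therapy within 5 days after enrollment (Section 3.8). Age is the interval from test to Cycle 1 Day 1 plus the interval from Cycle 1 Day 1 to Cycle 2 Day 1.
- Test at the start of therapy: 0 + 28 = **28 days**.
- Test at the limit of the 7-day rule: 7 + 28 = **35 days**.
- Test 7 days before enrollment and therapy 5 days after it: 7 + 5 + 28 = **40 days**.

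The third case arises because the recheck list for values older than 7 days (Sections 4.0 and 8.1) covers blood counts, liver tests and creatinine but not the pregnancy test. Whether 35 or about 40 days is the upper limit depends on whether the 7-day rule or that list is taken to govern.

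Against the 7-day limit applied before Cycle 1, the ratios are 28/7 = 4, 35/7 = 5 and 40/7 ≈ 5.7. Each day of delay adds one day. No general latest start for Cycle 2 is given, and Section 6.1.1 lets some patients proceed after failing to recover counts by day 43.

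**3. Number of patients.** Table 17 plans 13 + 3 = 16 females among 36, a share of 16/36 = 0.444.
- At the expected maximum of 22 patients: 22 × 0.444 ≈ 9.8 females.
- At the absolute maximum of 36: 16 females.
- If the equal age split intended in Section 11.1 held among girls, about half would be aged 12–17: 4.9 and 8.

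Post-menarchal girls under 12 are outside those last two counts. The documents do not say how many girls will be post-menarchal or will continue to Cycle 2.

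**4. GGT (minor).** Section 5.5.1.1 exempts a Grade 3 rise in ALT, AST or GGT from being a dose-limiting toxicity (DLT) if it recovers to Grade 1 or lower before the next cycle. Appendix III grades GGT. An attributable Grade 4 rise, or a Grade 3 rise that does not recover in time, is therefore a DLT. Table 8 orders creatinine, ALT and bilirubin; TDM item g orders ALT, AST and bilirubin. Scheduled GGT measurements: 0. First detection of an isolated GGT rise rests on local testing.

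**The case against.** The strongest reply is that the protocol may not intend the pregnancy criterion to be re-applied at Cycle 2. Section 4.0 cannot be met wholesale then: 4.1.7.1.j bars prior uproleselan, and the marrow-relapse definition in 4.1.4.1 needs at least 1% blasts, while Section 5.2 itself provides for patients in MRD-negative remission. Section 4.2.2 is worded as an entry rule, and the text under Table 1 names organ function only. Table 8 and item i agree with each other, which could reflect a deliberate choice. There are also safeguards: two effective contraceptive methods or abstinence, removal for pregnancy, discretionary testing, and a PRE row from which a site might well test.

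Much of this stands. A reader might infer that Section 5.2 plainly re-imposes the pregnancy exclusion before Cycle 2. The documents do not support so firm a reading, and part of the defect is loose wording in 5.2. But the case does not need it: 9.1.8 and 10.1(i) apply whichever reading is taken, and both depend on knowing the pregnancy status. Contraception is required from entry too, and the protocol still demands a test there. The discretionary entry sits under During Cycle 2, not before dosing. The PRE row conflicts with item i's own wording, so a site cannot tell which governs.

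On GGT, a reader might infer that a missed DLT could change the dose decision with some calculable probability. The documents give no frequency for isolated GGT elevation and no rate for other DLTs, so no such figure can be supported. GGT appears only inside an exclusion, TDM item g checks ALT, AST and bilirubin weekly in Cycle 1, and GGT is not in the uproleselan adverse event list in 9.1.10.

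**Conclusion.** The gap is real. Neither Table 8 nor TDM item i requires a pregnancy test before Cycle 2, and the only text pointing the other way, the PRE row of the shared grid, conflicts with item i. The last clearly required test is at least 28 days old at Cycle 2 Day 1. The upper figure is 35 days under the 7-day rule, or about 40 days if the recheck list is taken as exhaustive, before any delay. These ages assume that Cycle 2 starts no earlier than 28 days after Cycle 1 Day 1.

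Few patients are affected, and the documents give no pregnancy rate, so the number of exposures prevented cannot be estimated. The recommendation rests on the protocol's own prohibition and its stated fetal risks. The GGT omission is a minor inconsistency in how a DLT would be detected, with no quantified consequence.

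**What to change.** **Pregnancy test.** Require a negative test in post-menarchal patients within 72 hours before Cycle 2:
- In Table 8, mark the test under Prior to Cycle 2 with footnote 3, and change the timing in footnote 2 to *before each cycle*.
- Reword TDM item i so that the pregnancy test is due *prior to Cycle 1 and prior to Cycle 2*. This also removes the conflict with the PRE row.

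The cost is one test per continuing post-menarchal patient. If enrollment reached 36 with the Table 17 sex split, this could not exceed 16 tests at one each. For ages 12–17 alone it would be about 5 (at 22 patients) to 8 (at 36) on the assumptions shown.

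**GGT (minor).** Choose one of two:
- Add GGT to the existing liver draws: baseline, Days 7, 14, 21 and 28, and before Cycle 2. That is at most 6 results per patient with no extra venipuncture.
- State in 5.5.1.1 that isolated GGT elevation is not a DLT. This needs no tests, but an isolated Grade 4 rise would no longer count.

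Deleting the word GGT alone would not serve. GGT would stay under the general Grade 3 or greater rule and lose its recovery exemption.

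Neither change alters sample size or the dose-finding rules, apart from what counts as a DLT if the second GGT option is chosen.
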